9.2 Correlative Assays in Tumor Tissue

Tumor biopsies (mandatory when deemed safe and feasible) will be collected for research from adult patients (≥ 18 years of age).

Pharmacodynamic Analysis (ImmunoPD)

Pharmacodynamic assays will be performed on these tumor specimens to evaluate the effect of atezolizumab on immune cell components of the tumor and microenvironment. The results of these assays will help to elucidate the mechanism of action of atezolizumab in sarcoma and demonstrate the impact of a PD-L1 inhibitor on signaling pathways mediating the immune response. Efforts will be made to correlate any observed treatment-induced changes with clinical response or resistance to therapy.

Activated CD8⁺ T cells will be defined by the expression of TCR activation (Zeta chain phosphorylation) or phosphorylated Zap70 (pY493); CD8⁺ cells present within the tumor section that are positive for these markers will be quantified. Other targets of PD assays will include PD-L1 and PD-1 levels in cells present in the biopsy, suppressive immune checkpoint signaling (SHP1/SHP2 phosphorylation), CD4, and a tumor marker (e.g., β -catenin) to identify tumor region.

These biomarkers will be measured through multiplex immunofluorescence assays designed and validated by PADIS (See Section [2.5](#)). Measurements on the Nikon A1/Definiens platform will include cell enumeration and proximity of tumor cells (by pathology analysis and tumor marker IFA) to T-cells. Monoclonal antibodies to all markers have been validated by the standard PADIS approach, and PADIS has previously validated and reported on the tumor cell marker set.

Genetic Analysis

We will also perform exploratory genomic sequencing (WES and RNA-Seq) on biopsy tissue, with the goal of identifying potential correlations between atezolizumab activity and tumor genomic alterations (such as those involved in relevant immune pathways, neoantigen presentation, *etc.*). MSI status and mutational signatures may also be assessed. We will assess whether changes in the genomic makeup of the tumor is associated with treatment response and/or progression, and whether TMB correlates with patient outcome. Germline DNA obtained from PBMCs will be used as a point of comparison to identify somatic mutations. In addition to evaluating changes in tumor mutations over time (post-treatment), extensive molecular characterization of pre-treatment tumor biopsy tissue from each patient enrolled on this trial will enable identification of valuable potential biomarkers to predict which patients are more or less likely to respond to treatment.

At progression (or pre-progression, following any restaging at which a 10-19% increase in tumor volume is observed), tumor tissue from the optional biopsy will also be analyzed by the CLIA-certified OCAv3 assay, and an Oncomine report will be returned to patients to inform future treatment.

9.2.1 Timing of Tumor Biopsies

Biopsies will be collected from adult patients at:

- Baseline
- Prior to Cycle 3 Day 1 (± 3 days). If, at any point before Cycle 3 Day 1, there is clinical evidence that the patient is responding to drug, the biopsy will be conducted then instead of at the Cycle 3 Day 1 (± 3 days) timepoint.
- *Optional*: Day 1 (± 2 days) of the cycle following any restaging at which a 10-19% increase in tumor volume is observed (according to RECIST v1.1 criteria) if the patient has been on study for at least 4 cycles (the “restaging follow-up biopsy”), or at time of disease progression

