1.2 Secondary Objectives

- 1.2.1 Determine duration of response (DOR) using RECIST v 1.1 and/or change in clinical symptoms (time frame: baseline until disease progression, death, loss to follow-up, initiation of another anti-cancer treatment, withdrawal of consent, or study termination)
- 1.2.2 Measure progression-free survival (PFS) time (time frame: baseline until disease progression, death, loss to follow-up, initiation of another anti-cancer treatment, withdrawal of consent, or study termination)
- 1.2.3 Assess the number of activated CD8⁺ T cells infiltrating the tumor before and after atezolizumab treatment, and correlate treatment-induced changes with clinical response

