Adult patients will undergo tumor biopsies for pharmacodynamic studies at baseline and prior to Cycle 3 Day 1 (± 3 days; or sooner if there is clinical evidence that the patient is responding to drug) such as at confirmation of PR. Blood specimens will also be collected at these and other timepoints. We plan to use these research samples to evaluate the pharmacological effect of atezolizumab on immune cell components of the tumor, the tumor microenvironment, and peripheral T cell populations which will help to elucidate the mechanism of action of this agent in sarcoma and demonstrate the impact of a PD-L1 inhibitor on signaling pathways mediating the immune response. As there are differences in biological characteristics among sarcoma subtypes, pharmacodynamic comparisons will only be made within the CS and CCS sarcoma cohorts, rather than CCS and CS samples being pooled for analysis. Efforts will be made to correlate any observed treatment-induced changes with clinical response or resistance to therapy.

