PADIS has demonstrated the use of this IFA in identifying and enumerating CD8+ T cells within tumor tissue that has been segmented using the tumor marker β -catenin. The number of activated CD8+ T cells present inside and outside of the tumor marker-positive area will be reported for biopsies collected at baseline and on Cycle 3 Day 1, as modulation of the tumor immune microenvironment is expected to require an extended response time frame. T-cell activation status will be determined through detection of pZAP70 and pCD3 ζ phosphorylation. This endpoint will be correlated with patient response to immunotherapy. Figure 4 shows the clinical feasibility of the immunoassay demonstrated in a tissue microarray core specimen.

[figure not shown]

Figure 4. Performance of the immunoPD IFA on T cells captured in a colorectal cancer tumor microarray (collected with an ischemia time of 5 minutes or less), demonstrating our ability to identify activated T cells in tissue specimens collected from patients under Developmental Therapeutics Clinic SOPs.

While there is evidence to suggest that PD-L1 expression is associated with response to anti-PD-1/PD-L1 checkpoint inhibitors, there are not enough data available to definitively establish PD-L1 as a predictive biomarker for atezolizumab response in sarcoma. PADIS immunoPD IFA panels will be used in an exploratory fashion to measure baseline expression of PD-L1 in responders and non-responders, as well as the effects of atezolizumab on PD-L1 expression in tumor cells and PD-1 expression in T cells. Multiplex IFA panels measuring these markers in conjunction with CD3, CD8, and β -catenin are in development.

Intracellular staining and flow cytometry assays evaluating the immune signaling and activation in peripheral T cells will also be performed on blood samples collected at select sites. Peripheral T-cell subsets will be identified using phenotypic surface markers CD3, CD4, and CD8.

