5. TREATMENT PLAN

This is a multicenter open-label phase 2 trial evaluating atezolizumab in adult subjects ≥ 18 years of age and in pediatric/adolescent subjects ≥ 2 years of age with advanced CCS or CS. Patients will be divided into cohorts based on histology upon enrollment. There will be three cohorts: histologically confirmed CCS (or EWSR1 translocation), conventional CS (grade 2 or 3), and dedifferentiated CS.

Patient evaluations will be performed throughout the study as described below. Baseline history, physical examination, laboratory evaluations, urinalysis, and EKG are to be conducted within 8 days prior to the start of protocol therapy. If protocol therapy is started within 8 days of these eligibility screening evaluations (see Section [3.3](#)), values from the screening evaluations may be used as baseline measurements; if >8 days have passed since the screening evaluations, the medical history, physical examination, laboratory evaluations, urinalysis, and EKG must be repeated prior to starting protocol therapy. Baseline imaging scans and ECHO must be done within 28 days prior to the start of protocol therapy.

History and physical examination will be done within 8 days of Day 1 of all cycles. Labs (serum chemistries and CBC with differential) will be performed at baseline as described above, on Cycle 1 Day 15 [± 1 day], and then up to 3 days before the start of each subsequent cycle (LDH and protein do not need to be checked again after baseline). TSH will be checked at baseline (within 8 days of Cycle 1 Day 1) and then up to 3 days before the start of each subsequent cycle. EKG will be repeated as clinically indicated after the baseline measurement described above.

Patients will have a CT scan at baseline (within 28 days prior to start of protocol therapy). Patients will undergo a CT scan and be re-evaluated for response at the end of Cycle 3 and every two cycles thereafter (every 3 cycles for patients on study for >1 year; every 4 cycles for patients on study for >2 years). Given the concern of pseudoprogression ("tumor flare"), patients that are clinically well may continue on therapy following RECIST progression if they meet the criteria outlined in Section 11.4.

Research biopsies (mandatory for adult patients at all sites) and blood samples for PD studies (mandatory for patients ≥ 12 years of age) will be collected as described in Section [9.2](#) and Section [9.3](#).

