10. STUDY CALENDAR

Eligibility screening evaluations (see Section [3.3](#)) are to be conducted within 8 days prior to patient enrollment, with the exception of informed consent, echocardiogram (ECHO), and imaging, which must be done within 28 days prior to patient enrollment. Baseline history, physical examination, laboratory evaluations, and EKG are to be conducted within 8 days prior to the start of protocol therapy. If protocol therapy is started within 8 days of the eligibility screening evaluations, values from the screening evaluations may be used as baseline measurements; if >8 days have passed since the screening evaluations, the medical history, physical examination, laboratory evaluations, and EKG must be repeated prior to starting protocol therapy. Baseline imaging scans and ECHO must be done within 28 days prior to the start of protocol therapy.

Each cycle is 21 days (± 3 days due to scheduling conflicts). The start of a new cycle may be delayed up to 2 weeks to accommodate scheduling conflicts and other unexpected events. In the event that the patient's condition is deteriorating, laboratory evaluations should be repeated within 48 hours prior to initiation of the next cycle of therapy.

	Pre-Study Screening	Cycle 1 Week 1	Cycle 1 Week 2	Cycle 1 Week 3	Cycle 2 Week 1	Cycle 3 Week 1	Cycles 4+ Week 1	Off Treatment
Atezolizumab ^a		A			A	A	A	
Informed consent	X							
Demographics	X							
Medical history	X	X ^j						
Concurrent meds	X	X-----X						
Physical exam ^b	X	X ^j			X	X	X	X
Vital signs	X	X ^j			X	X	X	X
Height	X							
Weight	X	X ^j			X	X	X	X
Performance status	X	X ^j			X	X	X	X
CBC w/diff, plts ^c	X	X ^j			X	X	X	X
Serum chemistry ^c	X	X ^j			X	X	X	X
TSH ^d	X	X ^j			X	X	X	X
EKG ^e	X	X ^j						
Echocardiogram ^e	X	X ^j						
Adverse event evaluation		X-----X						X
Tumor measurements ^f	X	Tumor measurements are repeated every 6 weeks. Documentation (radiologic) must be provided for patients removed from study for progressive disease.						X
B-HCG ^g	X	X ^j			X	X	X	
Biopsy ^h		X				X ^h		X ⁱ
Blood for PD ^k		X		X ^k	X	X	X	X
Blood for genetics ^l		X	Blood for ctDNA analysis at C2D1, at the time of any biopsy, at the first two restagings (end of C3 and end of C5), and every two restaging visits after that (e.g., C9, C13, etc.)					X

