11. MEASUREMENT OF EFFECT

11.1 Antitumor Effect – Solid Tumors

Patients should be re-evaluated for response at the end of Cycle 3 (before Cycle 4), and at the end of every two cycles thereafter (before every even-numbered cycle). Restaging scans may be performed less frequently for patients on study for more than 1 year (every three cycles for patients on study for more than 1 year; every four cycles for patients on study more than 2 years). Confirmatory scans should also be obtained ≥ 4 weeks following initial documentation of objective response.

Response and progression will be evaluated in this study using the international criteria proposed by the revised Response Evaluation Criteria in Solid Tumors (RECIST) guideline (version 1.1) [59]. Changes in the largest diameter (unidimensional measurement) of the tumor lesions and the shortest diameter in the case of malignant lymph nodes are used in the RECIST criteria.

Patients that are clinically well may continue on therapy following RECIST progression with new lesions or increase in target lesions, provided the criteria in Section [11.4](#) are met.

Response will also be explored using iRECIST (see Section [11.3](#)). Increasing clinical experience indicates that traditional response criteria such as RECIST may not be sufficient to fully characterize activity in the new era of target therapies and/or biologics. In studies with therapeutic antibodies, complete response, partial response, or stable disease has been shown to occur after an increase in tumor burden, characterized by progressive disease by traditional response criteria. Therefore, conventional response criteria may not adequately assess the activity of immunotherapeutic agents because progressive disease (by initial radiographic evaluation) does not necessarily reflect therapeutic failure. Long-term effect on the target disease must also be captured. The iRECIST criteria, by incorporating specific response patterns

that have been observed with immunotherapeutic agents, have been developed to address these issues and provide standardized response criteria for use with immunotherapy [60].

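### Apparent early response can move the on-treatment biopsy forward, so time on drug can differ between the responder groups that Section 13.3 compares, and no planned analysis accounts for it

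*Combined protocol and SAP*

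**What the plan says.** Adults have a baseline biopsy and one on-treatment biopsy, planned before C3D1 (± 3 days). Section 9.2.1 adds an exception that operates at any point before C3D1: on clinical evidence that "the patient is responding to drug, the biopsy will be conducted then instead of at the Cycle 3 Day 1" timepoint. The early sample replaces the C3D1 sample and is not an extra one. The Précis, the Schema, Section 2.5 and Study Calendar footnote h carry the same exception. The C3D1 blood draw for ctDNA has a parallel clause in the Schema, the Section 9.1 biomarker table, Section 9.3.1.1 and calendar footnote l.

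Secondary objective 1.2.3 is to measure activated CD8+ T cells before and after treatment and "correlate treatment-induced changes with clinical response". Section 13.3 turns this into a within-cohort comparison of change from baseline between clinical responders and non-responders. It states 86% power for a 2.5 SD difference with 10 evaluable pairs at one-sided 0.01. It does not mention time on drug or early biopsies.

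Section 2.5.1 explains the C3D1 time by saying that "modulation of the tumor immune microenvironment is expected to require an extended response time frame".

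The only example of a trigger is in Section 2.5: "or sooner if there is clinical evidence that the patient is responding to drug) such as at confirmation of PR". Section 5 has patients "re-evaluated for response at the end of Cycle 3 and every two cycles thereafter", and Section 11.1 asks for confirmatory scans at least 4 weeks after a response is first documented.

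**The concern.** Apparent response helps to set when the second sample is taken, and response is also the grouping variable of the comparison. If the marker changes with time on drug, as the plan itself expects, part of any observed group difference may reflect when patients were sampled. That could hide a real difference or produce one where none exists. Because the early biopsy replaces the C3D1 biopsy, the sample that would have been comparable is never taken and cannot be recovered in analysis.

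Responders will be few. Section 13.1 calls a cohort positive at 3 responses in 17, so a single early biopsy can carry visible weight. The trigger is also left to undefined clinical judgement, which can vary between sites.

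**Working it through.** **1. Can the example trigger occur before C3D1?** Inputs: 21-day cycles (Section 10), first scan at the end of Cycle 3 (Sections 5 and 11.1), confirmation at least 4 weeks later (Section 11.1).
- C3D1 = 1 + 2 × 21 = day 43; the upper edge of the window is day 46.
- End of Cycle 3 = 3 × 21 = day 63.
- Earliest confirmed partial response = 63 + 28 = day 91.

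The calendar table also has a line giving tumor measurements every 6 weeks. On that reading the earliest confirmation is about 42 + 28 = day 70, still after C3D1. The example cannot trigger an early biopsy on either schedule.

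**2. Reproducing the stated power.** Inputs from Section 13.3: 10 pairs, difference 2.5 SD, one-sided 0.01 (z = 2.326). The plan states neither the test nor the split. Assume 25% responders, the design alternative in Section 13.1, which gives 2.5 and 7.5.
- Power = Φ(δ × √(n1·n2/(n1+n2)) − 2.326)
- √(2.5 × 7.5/10) = 1.369
- Φ(2.5 × 1.369 − 2.326) = Φ(1.097) = 86.4%, against the stated 86%.

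This takes it that the groups do not differ in time on drug.

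**3. Effect of a timing shift.** Let b be a shift in the group difference, in SD, caused only by sampling time. The documents give no time course, so every b is an assumption. The shift is treated as a constant, and any added spread is ignored.
- Power if the shift hides a true 2.5 SD difference: Φ((2.5 − b) × 1.369 − 2.326)
- One-sided type I error if it imitates a difference: Φ(b × 1.369 − 2.326)

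| b (SD) | Power | Type I error |
|---|---|---|
| 0 | 86.4% | 0.010 |
| 0.25 | 77.5% | 0.024 |
| 0.5 | 66.0% | 0.050 |
| 1.0 | 39.3% | 0.169 |

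A t-test with a 3:7 split starts lower and shows the same pattern: power 74.8%, 64.7%, 53.3% and 30.5%; type I error 0.010, 0.022, 0.043 and 0.134.

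**4. How many early biopsies matter?** Assume 3 responders and 7 non-responders, and that each early biopsy is off by 1 SD. √(3 × 7/10) = 1.449.
- None early: Φ(2.5 × 1.449 − 2.326) = 90%.
- One of three early: shift 1/3 = 0.33 SD, power about 79%.
- Two of three early: shift 2/3 = 0.67 SD, power about 63%.

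**5. Days or doses?** Cycle 2 starts on day 22. A biopsy before that dose follows one infusion. A biopsy after it and before the Cycle 3 dose follows two, the same number as a pre-dose C3D1 biopsy, and differs only in days.

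**The case against.** The strongest reply is that the exception may rarely or never be used. Its trigger is early clinical evidence, whereas the grouping variable is presumably RECIST response, first assessed after C3D1. Only responders with early signs would be moved, and some patients moved on a false alarm would end up among the non-responders. This stands. A reader might infer that the comparison is confounded as a matter of fact; the documents show only that it can be.

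A reader might also infer that early sampling must understate the change in responders, because Section 2.5.1 expects the effect to take time. That section justifies the general time point. It does not say that a patient already showing clinical response has less immune change at that moment. Sampling at apparent response could equally catch a peak.

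The obvious remedy, striking out the early biopsy, has its own cost. Section 9.2.2 reports that about 20% of research biopsies are unusable and that pairs are needed. Making fast responders wait may lose their tissue, and analysing only C3D1-window pairs removes those same patients. Either choice makes loss of pairs depend on response. This stands too, and it argues for showing both analyses.

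Some information is already collected. Section 9.2.4 puts collection date and time on each biopsy label, so time on drug can be recovered. However, Section 13.3 plans no use of it, and the cycle-by-cycle blood immune assays at the NCI site do not replace tumor data. The ctDNA clause matters less: that work is exploratory, has other draws, and Section 9.3.1.1 commits at minimum only to pre-treatment samples and those at restaging scans suggesting growth.

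**Conclusion.** The concern holds in a limited form. A stated rule lets apparent response change the time of the on-treatment biopsy, and the powered comparison in Section 13.3 is grouped by response, for a marker that the plan treats as time-dependent. Time on drug can therefore differ systematically by group, and nothing in the analysis plan deals with it.

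Neither the size nor the direction of the bias follows from the documents. The 66% power and 0.05 type I error rest on an assumed 0.5 SD group shift, a normal approximation and an assumed 2.5:7.5 split. They show how sensitive the comparison is and do not predict what will happen. How often the exception will be used is unknown.

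One part needs no assumption beyond the planned schedule: the example in Section 2.5 cannot occur before C3D1, so Sections 2.5, 9.2.1 and 11.1 must be reconciled. The effect is confined to the secondary and exploratory biomarker comparisons; the primary response-rate analysis is unaffected.

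**What to change.** **Timing rule.** Make the C3D1-window biopsy, taken before the Cycle 3 dose as the Cycle 3 collection sheet in Appendix E states, the default for all adults. If the early biopsy is kept, define its trigger and use the same definition in Section 9.2.1, the Précis, the Schema, Section 2.5 and calendar footnote h. Remove or replace the confirmed-response example. Treat the ctDNA clause likewise in the Schema, the Section 9.1 table, Section 9.3.1.1 and footnote l. Section 9.2.1 words the rule differently from the other places, so each needs its own edit. Record the reason for any early biopsy as well as the day.

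**Section 13.3.** Pre-specify:
- days and doses on drug at biopsy, reported by response group (Section 10 lets cycle starts slip up to 2 weeks, so C3D1 is not a fixed day either);
- early biopsies identified separately;
- the responder versus non-responder comparison given both with all pairs and with C3D1-window pairs only;
- no conclusion of a difference that rests on early biopsies alone.

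**Cost.** Wording changes, one extra recorded item and slightly more analysis, with no added procedure. The restricted comparison will have fewer responders and may itself select on response, so both results must be shown. Adjusting for time on drug in a model would be weak with about 10 pairs.

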9.2.2 Tumor Biopsy Procedure

Serial tumor biopsies will be obtained by the Interventional Radiology team by a cutaneous approach, a dermatologist for skin lesions, or an ENT for lesions that are easily biopsiable through ENT exam. The investigators will meet regularly with the Interventional Radiology team to review patient scans and discuss patients’ medical history. If a site is deemed appropriate for biopsy with minimal risk to the participant by agreement between the investigators and the biopsy team, an attempt for biopsy will be made. Because approximately 20% of tumor biopsies collected on research trials are not usable due to the presence of stroma or normal and/or necrotic tissue and paired biopsies are necessary for analysis, up to 5 core biopsies ≥ 18 -gauge in diameter and ≥ 1 cm in length, or equivalent, will be obtained during each procedure to try and ensure adequate tumor content and quality. If possible, the lesion from which each biopsy is taken, and whether the specimen came from the center or periphery of the lesion, will be documented.

Acceptable biopsy procedures are:

- Percutaneous biopsy with local anesthetic.
- Excisional cutaneous biopsy with local anesthetic
- Other biopsy with local anesthetic and/or sedation that has been shown to have a risk of severe complications $< 2\%$. *Note*: This risk determination is made by the interventional radiologist after determining the complication rate for the patient through discussion of the patient’s scans and medical history with the investigators.

The use of imaging to facilitate biopsies will be decided by members of the biopsy team and may include ultrasound, CT scan, or MRI. Should a CT scan be needed for biopsy, the number of scans for each procedure will be limited to the minimum number needed to safely obtain a biopsy. Tumor biopsies and local anesthesia will be administered only if they are considered to be of low risk to the participant, as determined by the investigators and the biopsy team. Cores from different areas of the tumor are preferred when feasible. The clinical, radiologic, and pharmacodynamic members of the research team will meet monthly to review the adequacy of the biopsy specimens for analysis.

Baseline biopsies will be performed following patient enrolling on study. If an initial attempt at a baseline biopsy is unsuccessful, the patient will be given an option to proceed with a repeated

attempt. A separate consent form must be signed for each biopsy procedure, so patients may choose not to undergo subsequent biopsies. If the baseline biopsy is unsuccessful or the patient refuses to undergo subsequent biopsies, no further biopsies will be performed but the patient will remain on study, receive study medication, and other correlative studies will be performed.

